barriers and facilitators of integrating TASSH into the HIV clinics for management of HTN; an **implementation phase**, during which we will compare, in a cluster RCT of PHCs and among 960 HIV+ patients with uncontrolled HTN, the effect of PF versus a self-directed condition (i.e. receipt of information on TASSH without PF) on systolic BP reduction at 12 months (primary outcome); and a **post-implementation phase**, in which we will use RE-AIM to compare the effect of PF vs. self-directed condition on adoption and sustainability of TASSH at 12 and 24 months respectively (secondary outcomes). We will also assess the mediators of the adoption and sustainability of TASSH at 12 and 24 months. Components of the PF strategy will include: (a) Formation of an advisory board of key stakeholders at all levels of care

including the Lagos State AIDS Council Agency, who will provide leadership support for adaptation and integration of TASSH into HIV clinics. The board will provide leadership support for the adaptation and integration of TASSH into HIV clinics; **(b)** Use of a train-the-trainer model [from our previous trials],^{19, 30} to train a cadre of experienced nurses from the Lagos State Directorate of Nursing to serve as practice outreach facilitators (POFs); and **(c)** Training of the HIV clinic nurses on the TASSH protocol for BP measurement, CV assessment, initiation of treatment with antihypertensive medications, and referral of complicated cases. As shown in **Figure 1**, all 30 HIV clinics enrolled during the pre-implementation phase, will be randomly assigned to either the PF intervention (N=15) or the self-directed condition (N=15). Once randomized, the clinics will participate in the 12-month implementation phase (intervention period) followed by a 12-month post-implementation period to assess its intervention sustainability. The primary outcome is *change in systolic BP* from baseline to 12 months. The secondary outcomes are *adoption* [proportion of patients who were correctly diagnosed with HTN, received lifestyle counseling and antihypertensive treatment]; and *sustainability* [maintenance of TASSH uptake at the HIV clinics at 24 months].

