The study implementation phase will be conducted at 30 HIV clinics located in Lagos, Nigeria. Sites and participants for the proposed study will be recruited from the list of over 67 HIV clinics registered with the Lagos State Healthcare Board. The NIMR will recruit 960 patients from 30 HIV clinics from this list under the guidance of Lagos State AIDS Control Agency, which funds comprehensive care for its HIV patient network in Lagos State. Note that this means recruitment of about 32 participants at each of the HIV clinics. Eligibility criteria for study participants are outlined below.

Inclusion criteria

- Be an adult aged 18 years and older.
- Attends one of the 30 HIV clinics.
- Have a diagnosis of HTN with uncontrolled blood pressure, i.e. BP is 140-179/90-100 mm Hg.
- Ability to provide consent.

Exclusion criteria

- BP>180/110 mm Hg;
- history of chronic kidney disease, heart disease, diabetes
- Stroke,
- pregnancy
- Inability to provide informed consent.
- Refusal to participate in the study.

Screen Failures

Screen failures will be referred to the PHCs for further management as is done in routine practice.

Strategies for Recruitment and Retention

The research staff will conduct the screening, consent, enrollment, and all study assessments. The study will recruit 30 HIV clinics from the network of 67 HIV clinics, who are part of the 100 primary care practices managed by the Lagos State Healthcare Board (LSPHB). All 67 HIV clinics are affiliated with the Lagos State AIDS Control Agency, which utilizes LSPHB to provide comprehensive primary care services to PLWH. Eligible HIV clinics will be selected from areas geographically distinct from one another. Once a clinic agrees to participate, their director will be asked to sign an MOU and identify 2 HIV nurses to be trained. Eligible patients will be identified from the HIV clinics during routine visits. Each clinic will recruit 32 patients using these inclusion criteria: 1) patient receiving care at the clinic; 2) adults 40 years and older; 3) BP 140-179/90-100 mm Hg; and 4) can provide informed consent. Exclusion criteria: 1) BP>180/110 mm Hg; history of chronic kidney disease, heart disease, diabetes or stroke, pregnancy; 2) inability to provide consent; and 3) refusal to participate.

SECTION 4: Study Intervention

Description of Study Intervention and its Administration

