All 30 HIV clinics enrolled will begin the study as part of the pre-implementation phase for 12 months, after which they will be randomly assigned to either the PF intervention (N=15) or the self-directed condition (N=15). Once randomized, the PHCs will participate in the 12- month implementation phase (intervention period) followed by a 12-month post- implementation period to assess its sustainability.

Randomization will occur in 5 cohorts of 6 PHCs every 6 months for 30 months and will be stratified by cohort to ensure balance over time. Upon completion of recruitment for each cohort, the clinics will be randomized in a 1:1 ratio to either the PF intervention or self-directed condition (i.e. receipt of information on TASSH implementation without PF). The sequence of randomization will be generated by [name], and kept in secure electronic format inaccessible to study sites, in accordance with CONSORT guidelines. Sites will be

informed of their randomization group by telephone. Because of the nature of the intervention, it is impossible to blind the patients, lay health advisors, and the study coordinators to the group assignment. The data analysts will remain blinded to treatment assignment until the completion of the implementation phase, defined as the period from baseline to 12-month follow-up(primary endpoint). During the post-implementation phase, the practice facilitators will leave the intervention sites and will have minor direct influence on the TASSH adoption. As the intervention concludes, data analysts will be unblinded following the primary endpoint. Preliminary database containing baseline and 12-month follow-up data will be locked upon unblinding for analysis.

Study intervention compliance (Group A).

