For adoption, the analysis will have one within person factor – Time (baseline and 12-month coded naturally as months [0 and 12]) – and one primary between-patient factor – (Randomization Group dummy coded as 0 = Self-directed Condition and 1 = Practice Facilitation). Fixed effects will be specified for time, randomization group and their interaction effect (group by time). The outcome measure will be a composite index for adoption of TASSH (defined as patients diagnosed with HTN, received lifestyle counseling and treatment for HTN by the HIV nurses). Additionally, the nurses will be nested within clinics creating a 3-level analytic model (observations nested within nurses nested within clinics). Random effects will be specified for clinics and for nurses, adjusting for the clustering of measures within nurse and nurses within clinic. Multilevel modeling software (SAS, Version 9, PROC MIXED) will be used to compute full information maximum likelihood (FIML) estimates of the model parameters. The PROC MIXED procedure will use an error structure that allows for the possibility of group differences in (a) the error variances at 12 months; and (b) the serial correlations of the baseline with the 12-month outcomes. For sustainability, the analysis will be repeated as described above but will be evaluated at 24 months instead of 12 months. Adoption at 12 months will be assessed using questionnaires completed by nurses and sustainability at 24 months will be assessed with site interviews and site visits. Levels of adoption and sustainability will be compared between the group that randomized to the PF intervention and the group randomized to the self-directed condition. The qualitative components of sustainability at 24 months will be assessed using interviews with nurses and clinic leadership. These interviews will be recorded, transcribed and entered into NVIVO Version 11 for analysis. The analytic plan will be similar to the qualitative methods described for Aim 1.

Analysis for Aim 4

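### Aim 3 is to be fitted by full maximum likelihood on 30 clinics with no small-sample correction, so its standard errors are slightly too small; the clinic-by-time effect also needs stating

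*Combined protocol and SAP*

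**What the plan says.** - **Estimator.** Under Statistical Considerations, Analysis for Aim 3, PROC MIXED in SAS Version 9 "will be used to compute full information maximum likelihood (FIML) estimates of the model parameters".
- **Fixed effects.** Time (0 and 12 months, or 24 months for sustainability), randomisation group and their interaction.
- **Random effects.** "Random effects will be specified for clinics and for nurses, adjusting for the clustering of measures within nurse and nurses within clinic". No random slope and no clinic-by-time term is named.
- **Residual structure.** It "allows for the possibility of group differences in (a) the error variances at 12 months; and (b) the serial correlations" of baseline with the 12-month outcome.
- **Clusters.** Under Randomization, Measures to minimize bias, and Blinding, the 30 clinics are allocated 1:1, 15 per arm.
- **Nurses.** Under Strategies for Recruitment and Retention, once a clinic joins, "their director will be asked to sign an MOU and identify 2 HIV nurses to be trained". That gives about 60 nurses.
- **Unit of analysis, second description.** The overview that opens Statistical Considerations describes Aim 3 differently, as a multilevel mixed model with an unstructured covariance matrix whose outcome is the proportion of participants within a clinic.
- **Not stated for Aim 3.** Significance level, ICC, denominator degrees of freedom, and any small-sample correction.

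**The concern.** The clinic is the unit of randomisation, and there are only 30. Full ML estimates variance components as if the fixed effects were known, so the variances are biased downward, and with few clusters the bias reaches the standard errors. REML removes it, and the software already named offers REML with Kenward-Roger degrees of freedom. As written, confidence intervals and p-values for adoption and sustainability lean towards finding a difference. These are secondary outcomes, but they are the main implementation results of a hybrid type II trial, and they carry into the Aim 4 path model.

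The choice of random effects raises a second question. Facilitation is delivered to a whole clinic. If clinics differ in how much they change, the group-by-time contrast should be judged against that variation, and the Aim 3 text names no term that captures it.

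**Working it through.** The plan states no standard error, power or ICC for Aim 3, so there is no figure of its own to reproduce.

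**Inputs.** From the documents: 30 clinics (15 + 15), 2 nurses per clinic, two time points, full ML. Assumed: two-sided 5%, balanced data, normal outcome, variances pooled across arms, and the ICCs shown below.

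**1. Standard error.** In a balanced design ML divides the relevant sum of squares by n and REML by n − p, so the ratio of ML to REML standard error is √((n − p)/n).

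- Clinic-level or 12-month comparison (n = 30, p = 2): √(28/30) = 0.966, which is 3.4% too small.
- Group by time with clinic and nurse intercepts only: the clinic effect cancels from each nurse's change. What remains is 60 nurse changes with p = 2: √(58/60) = 0.983, which is 1.7% too small.

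**2. Type I error.** This is 2 × P(t on n − p df > critical value × ratio).

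| Test | Reference | ML | REML |
|---|---|---|---|
| Clinic-level, n = 30 | t28: 2.048 × 0.966 = 1.979 | 5.8% | 5.0% |
| Clinic-level, n = 30 | normal: 1.960 × 0.966 = 1.894 | 6.9% | 6.0% |
| Group by time, 60 nurse changes | t58: 2.002 × 0.983 = 1.968 | 5.4% | 5.0% |
| Group by time, 60 nurse changes | normal: 1.960 × 0.983 = 1.927 | 5.9% | 5.5% |

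Simulation of the 12-month comparison (40,000 trials per setting, ICC 0.1 to 0.8) gave 5.0–5.9% for ML with t28 and 6.0–6.9% with a normal reference. REML gave 4.4–5.0% and 5.3–6.1%.

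**3. The clinic variance component.** The factor 28/30 applies to the variance of clinic means, not to the clinic component itself. In the same simulation the ML estimate of that component was 0.63, 0.86, 0.90 and 0.93 of the true value at ICC 0.1, 0.3, 0.5 and 0.8. REML gave 0.99–1.00.

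**4. No clinic-by-time effect.** Suppose two nurses in a clinic have changes correlated at ICC ρ, but the model treats them as independent. The variance of the contrast is then understated by a factor of 1 + (2 − 1)ρ. In large samples the type I error is 2 × P(Z > 1.96/√(1 + ρ)):

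- ρ = 0.2: 1.96/1.095 = 1.789, giving 7.4%
- ρ = 0.5: 1.96/1.225 = 1.600, giving 11.0%
- ρ = 0.8: 1.96/1.342 = 1.461, giving 14.4%

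Simulation at the actual size (30 clinics × 2 nurses, 200,000 trials) gave:

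| Assumed ρ | ML, t58 | REML, t58 | REML with clinic-by-time, t28 |
|---|---|---|---|
| 0.2 | 7.9% | 7.4% | 4.8% |
| 0.5 | 11.9% | 11.3% | 5.0% |
| 0.8 | 15.7% | 15.0% | 5.0% |

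Moving from ML to REML recovers only 0.5 to 0.7 points here. The clinic-by-time term with clinic-based degrees of freedom recovers nearly all the rest.

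**The case against.** The strongest reply is that full ML on its own does little harm. It adds 0.8 points of type I error on a clinic-level test with t28 and 0.4 points on the group-by-time test with t58. The plan nowhere commits to a normal reference, and where one is used REML would already give 6.0%. All of this stands.

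A reader might infer that understated between-clinic variance is what distorts the group-by-time test. With clinic and nurse intercepts only, it does not: that variance cancels from the change, and the 1.7% shortfall comes from the residual variance.

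A reader might also blame the estimator for the 8–16% figures. They come almost entirely from omitting a clinic-by-time effect. They rest on ICCs that the documents do not give, and on reading the clinic and nurse effects as intercepts, which the text neither states nor excludes. If the outcome is one proportion per clinic per time point, as the overview of Statistical Considerations suggests, group by time is already tested against between-clinic variation in change and the problem does not arise. For sustainability, the Aim 3 text refers to site interviews and site visits, so a two-nurse layout at 24 months is itself uncertain.

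One defence does not stand, namely that full ML is needed for incomplete data. REML is also likelihood-based and rests on the same missing-at-random assumption that the plan adopts under Methods for handling missing data.

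**Conclusion.** The point holds in a modest form. Full ML with 30 clinics and no degrees-of-freedom method makes Aim 3 standard errors about 2–3% too small, always in the anti-conservative direction, and the excess type I error due to ML itself is under one percentage point. That would matter only for a borderline result.

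The unstated clinic-by-time effect could matter more: about 8%, 12% or 16% type I error at assumed ICCs of change of 0.2, 0.5 or 0.8. This is conditional on nurse-level data being analysed with intercepts only, and the plan's two descriptions of Aim 3 leave that open. All figures assume a two-sided 5% level, balanced data and a normal outcome.

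The documents do not support extending the criticism to the primary outcome. The Aim 2 section names a mixed model but no estimator, so nothing there is shown to be wrong.

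**What to change.** For Aim 3, before the analysts are unblinded:

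1. Replace FIML with REML and Kenward-Roger degrees of freedom (METHOD=REML, DDFM=KR), and state the significance level.
2. Reconcile the overview of Statistical Considerations with Analysis for Aim 3 on the unit of analysis: one proportion per clinic, or nurse-level observations. Do this for 12 and 24 months.
3. If nurse-level observations are analysed, add a clinic-by-time random effect so that group by time is tested against between-clinic variation in change.

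For Aim 2, naming the same estimator and degrees-of-freedom method would be sensible, but that is a suggestion and not a correction.

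The cost is a few lines of text and software options, with no change to design, data or sample size. Clinic-level intervals widen by about 3.5% (1/0.966) if t28 would have been used anyway, and by about 8% (2.048/1.894) against ML with a normal reference. If clinics in truth do not differ in change, the clinic-by-time model with t28 is mildly conservative (3.9% in simulation), a small loss of power.

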Assessment of Potential Risks and Benefits: Potential risks and benefits will be assessed at each study visit (Baseline, 6, 12, 24 months). Detailed assessment of risks and benefits is listed under Study Assessment and Procedures.

SECTION 3: Study Objectives

Primary objective, endpoint, and justification

The primary objective is to compare in a cluster RCT of 30 HIV clinics, the effect of PF intervention versus a self-directed condition (receipt of information for implementation of TASSH but no facilitation) on systolic BP reduction among 960 HIV patients with HTN (BP>140/90 mmHg).

The primary outcome is change in systolic BP (SBP) from baseline to 12 months. Following existing TASSH protocol, the SBP reduction in patients will be assessed as mean change in systolic BP from baseline to 12 months. Blood pressure will be taken with valid automated BP device as follows:

At baseline, three BP readings will be taken by trained research coordinators using an automated BP monitor with participant seated comfortably for 5 minutes prior to the measurements. The average of three BP readings will be used as the measure for each visit. The same procedure will be followed at the 12-month study visit.

Justification: Uncontrolled BP is defined as average clinic systolic BP>140 mmHg or diastolic BP>90 mmHg following the guidelines set forth by WHO for CVD treatment and in accordance to the Nigerian healthcare policy. Adopting these guidelines currently instituted within the Nigerian healthcare system will ensure sustainability of the proposed study's procedures.

Secondary objective, endpoint, and justification

The secondary objectives are to:

- Compare in a cluster RCT of 30 HIV clinics, effect of the PF intervention versus self-directed condition (receipt of information for implementation of TASSH but no facilitation) on TASSH adoption and sustainability.
- Determine the mediators of adoption and sustainability of TASSH across the 30 HIV clinics at 12 months and 24 months respectively.

Secondary outcomes are:

- Rate of adoption and sustainability of TASSH across the PHCs at 12- and 24 months respectively.
- The mediators of TASSH across the HIV clinics at 12 and 24 months.

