Implementation process measures

External change agent support is a 3-item tool that evaluates support provided by external facilitators, the expectations about performance and improvement, and the ways to achieve the goal of the project. Items are scored on a 5-point Likert scale and the Cronbach $\alpha=0.77$.

Organizational Readiness to Change105 (Facilitation Scale-8-items): which evaluates organizational capacity to facilitate change will be used to evaluate implementation process measures focused on CFIR Engaging construct. Each item measures the extent to which a respondent agrees or disagrees with the item statement on a 5-point Likert-type scale (1 = strongly disagree; 5 = strongly agree) and the Cronbach $\alpha=0.95$.

Safety and Other Assessments:

Some personal and sensitive information may be requested from the patients during the course of this research study. Patients do not have to answer any questions they choose not to. They might feel inconvenienced by giving their time for the study visits and meetings with community health officers. Because patients' blood pressure recordings and survey responses will be used as a source of data for this study, there is a potential risk of a violation of their privacy. The study team will take steps to ensure that their private information is kept in a secured and locked safe.

Potential Benefits:

The intervention will benefit the participants by improving their blood pressure control, reducing their cardiovascular risk profile, and increasing their role as active participants in the management of their HTN. The ultimate aim is to develop a facilitation strategy that can be delivered nationally at little expense; thus, the benefit to others will occur when the intervention becomes a routine part of activities at the PHCs. Overall, the benefits of understanding effective methods for helping vulnerable populations, i.e. people living with HIV (PWH), reduce their cardiovascular risk far outweigh the remote possibility of a breach of confidentiality. The study may also have relevance to other PHCs by testing new strategies to enhance implementation of evidence-based interventions for improving hypertension control in high-risk populations.

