This aim will assess the extent to which inner setting variables (e.g., implementation leadership, implementation climate, and organizational culture) affect the degree of adoption of TASSH as defined in Aim 3, and its sustainability at 24 months. Particular attention will be paid to the pathways via which this occurs. We will estimate a just-identified path model using the robust weighted least squares estimator to investigate relationships among the theoretical mediators of implementation climate, implementation leadership, organizational culture, organizational readiness to change, and external change agent support. Based on our conceptual model, we will test the direct effects from the theoretical constructs to the adoption components (individually). In addition to the direct effects, the indirect effects from each variable to adoption via inner setting variables will be estimated as the product of component direct effects and tested using bootstrapped 95% confidence intervals. Finally, we will estimate the direct effects of the

predicted model of adoption on SBP reduction. Predicted probabilities of the adoption and sustainability outcomes and SBP will be calculated from path model coefficients to elucidate the magnitudes of direct and indirect effects.

Methods for handling missing data:

Although we will attempt to retain as high a fraction of participants as possible, we acknowledge that some attrition is likely, leading to missing outcome values. The generalized linear mixed models proposed for the primary and secondary analyses incorporate an assumption of data that are missing at random (MAR), meaning that the likelihood of a value being missing depends on observable characteristics (e.g., sex or age). In sensitivity analyses, we will assess the impact of different assumptions about the missing data mechanism, and will determine the robustness of trial results to these different assumptions. We will consider the use of multiple imputations of missing data as an alternative sensitivity analysis.

SECTION 7: Ethical Consideration

Institutional Review Board Approvals for this study will be obtained from the NYU School of Medicine (NYU) and the Nigerian Institute of Medical Research (NIMR).

Informed consent

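### The Aim 4 path model states no randomised-arm term, so construct-to-adoption paths may be confounded by arm and no mediated PF effect is estimated

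*Combined protocol and SAP*

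**What the plan says.** The Analysis for Aim 4 (Statistical Considerations) describes the model in these steps.

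- Model and estimator: "We will estimate a just-identified path model using the robust weighted least squares estimator".
- Variables: the purpose is to "investigate relationships among the theoretical mediators of implementation climate, implementation leadership, organizational culture, organizational readiness to change, and external change agent support".
- Direct paths: "Based on our conceptual model, we will test the direct effects from the theoretical constructs to the adoption components (individually").
- Indirect paths: "the indirect effects from each variable to adoption via inner setting variables will be estimated as the product of component direct effects", and these are "tested using bootstrapped 95% confidence intervals".
- A last step relates predicted adoption to SBP reduction.

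Randomised arm appears in none of these steps. The neighbouring models do contain it: Aim 2 has an arm-by-time interaction, and Aim 3 has "Randomization Group dummy coded as 0 = Self-directed Condition and 1 = Practice Facilitation".

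The Objectives set Aim 4 across all 30 PHCs, 15 per arm. Section 3 lists as a secondary outcome "The mediators of TASSH across the HIV clinics at 12 and 24 months". The opening of Statistical Considerations describes Aim 4 as examining mediators for the PF intervention.

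On one of the five constructs, Section 6 says: "External change agent support is a 3-item tool that evaluates support provided by external facilitators". Section 4 (usual care, Group B) says that control nurses get no facilitation.

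**The concern.** A variable that moves both a mediator and the outcome, and is left out, makes the mediator look influential when it is not. Here the protocol itself gives PF both roles.

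- **PF acts on the constructs.** The advisory board exists to give leadership support, and implementation leadership is a listed construct. External change agent support measures something only PF clinics are given.
- **PF acts on adoption by other routes.** Section 5 gives patients in PF clinics three-monthly nurse meetings for counselling and treatment, which are themselves components of adoption. Section 4 adds site meetings, target setting and performance feedback. None of these has to work through climate, leadership or culture.

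Two things are at stake. Aim 4 could report as drivers of adoption some constructs that only mark allocation. And because every stated indirect effect starts at a construct, the model as described would not show whether PF works through any of them. A just-identified model has no overall fit test that could reveal the omission.

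**Working it through.** The plan gives no effect size, power or sample-size figure for Aim 4, so there is nothing of its own to reproduce. Inputs from the documents are 30 clinics, 15 per arm, five constructs and a two-sided 5% level (from the 95% intervals). All PF shifts below are assumptions, in within-arm SD units. Linear regression with t-tests at clinic level stands in for weighted least squares with bootstrap intervals.

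**One mediator with no true effect, arm omitted.** Let dM be the PF shift in the mediator and dY the PF effect on adoption that does not pass through it. With 1:1 allocation the variance of arm is 0.25, so the expected false slope is approximately

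dM × dY × 0.25 / (1 + 0.25 × dM²).

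For example, with dM = dY = 1 this is 0.25 / 1.25 = 0.20. Rejection rates are simulated.

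| dM = dY (SD) | False slope | Falsely significant, arm omitted | Arm included |
|---|---|---|---|
| 0.5 | 0.0625 / 1.0625 = 0.06 | about 6% | 5% |
| 1 | 0.25 / 1.25 = 0.20 | about 19% | 5% |
| 1.5 | 0.5625 / 1.5625 = 0.36 | about 55% | 5% |
| 2 | 1 / 2 = 0.50 | about 89% | 5% |

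If dY = 0 or dM = 0 the formula gives zero, and the simulated rate is 5%.

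**All five constructs entered jointly**, closer to the planned model. None has a true effect. PF shifts the four ordinary constructs and adoption by the same amount, and shifts the support scale by 0, 1, 2 or 3 SD. Residuals are independent; 20,000 runs per case.

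| Shift in constructs and adoption | Support shift 0 / 1 / 2 / 3 SD: each ordinary construct | Support scale | At least one of five | At least one, arm included |
|---|---|---|---|---|
| 1 SD | 10 / 9 / 7 / 6% | 5 / 9 / 16 / 23% | 35 / 35 / 36 / 39% | about 21% |
| 1.5 SD | 14 / 13 / 10 / 8% | 5 / 8 / 15 / 24% | 48 / 46 / 45 / 45% | about 21% |

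The 21% with arm is ordinary multiplicity from five tests at 5% (1 − 0.95⁵ = 23% if independent). The excess over it is what omitting arm adds.

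The split depends on how many constructs PF moves. If it moves only one ordinary construct and the support scale, that construct's rate at 1 SD is about 17 / 13 / 8 / 6% for support shifts of 0 / 1 / 2 / 3 SD. At 1.5 SD it is about 36% (support shift 1 SD) and 11% (3 SD).

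**Cost of adding arm.** In the joint model, standard errors on the ordinary constructs rise by about 2% to 4%. The support scale's squared correlation with arm is 0.25d² / (1 + 0.25d²) for a shift of d SD: 0.50 at 2 SD and 0.69 at 3 SD. Variance inflation from that pair alone is 1 + 0.25d² = 2.0 and 3.25, so standard errors are 1.4 and 1.8 times those without the correlation.

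**The case against.** The strongest reply is that absence from the text is not exclusion. The quoted list is of mediators, and arm is an exposure. The paths rest on a conceptual model that the available text does not show, and Hypothesis 3 breaks off next to a missing figure. This stands: the supportable statement is that the plan does not state an arm term, and a reader should not infer that arm was deliberately dropped.

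A reader might also infer that any construct PF shifts will appear to drive adoption. The documents do not support that. Bias needs PF to reach adoption outside the modelled constructs, and even with a 1 SD shift a lone null mediator is non-significant about 81% of the time. Nor do the 55% and 89% figures describe the planned model: they are for one mediator alone under large assumed shifts. External change agent support partly stands in for arm and lowers the rates for the other constructs. It does not cure the problem, because part of the bias then moves onto the support scale.

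On timing, a reader might infer that direction can never be separated because mediators and outcomes share the 12- and 24-month points. That goes too far. Section 5 measures some organisational factors at baseline, and 12-month mediators precede 24-month sustainability. The gap is that the Aim 4 text does not say which time points enter the model.

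Finally, the Aim 4 objective speaks of mediators of TASSH adoption and does not promise to apportion the PF effect. That is fair, but the opening of Statistical Considerations ties the aim to the PF intervention, and Aim 4's value in a trial of PF lies in that link.

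**Conclusion.** The point holds in a limited form. As written, the Aim 4 model has no arm term. Since PF is designed to act on some constructs and has other routes to adoption, the construct-to-adoption paths may be biased away from zero, and no PF-to-mediator-to-adoption effect is estimated. The second consequence does not depend on how large the confounding is.

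Under the assumed shifts, the joint model gives about 6% to 14% false positives per ordinary construct and up to 24% for the support scale when PF moves all four ordinary constructs equally. Other patterns of shift change these rates. With small shifts (0.5 SD) the distortion of a single path is slight, and it is absent if PF acts on adoption only through the modelled constructs.

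This concerns a secondary mediator analysis. The primary SBP model and the Aim 3 adoption comparison both specify arm and are not affected. It is worth correcting because the better model uses data already planned.

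**What to change.** State the following in the Analysis for Aim 4:

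- Randomised arm is the exogenous variable, with a path to each mediator and a direct path to adoption, sustainability and SBP.
- The mediated effects reported are arm to mediator to outcome.
- Bootstrap intervals are obtained by resampling whole clinics within arm.
- For 24-month sustainability, the mediators are those measured at 12 months. Name the time point used for every other path.
- Results are labelled exploratory. Mediators are not randomised, so adjusting for arm does not remove other confounding between mediator and outcome.

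If the conceptual model already contains arm, showing its paths in the text would settle the first item.

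The cost is wording and a few more parameters, with no new data. Intervals widen slightly for most constructs and clearly for the arm and external-support paths (variance inflation about 2 to 3 if PF shifts support by 2 to 3 SD, assumed). With 30 clinics those two paths may be hard to tell apart, and the report should say so.
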